11.2 Statistical Analysis

Data from the two trials will be analysed and reported separately. Both trials have the same primary and secondary outcomes so the analysis and reporting will be similar. As both trials are pragmatic parallel group RCTs, data will be reported and presented according to the latest CONSORT guidelines. The statistical analyses will be performed on an intention-to-treat basis. Under the strict intention to treat (ITT) principle, all women will be included in the analysis once they are randomised as per the allocated treatment regardless of what happens after randomisation. All statistical exploratory tests will be two-tailed with alpha = 0.05.

Interim Analysis

There is no formal planned interim analysis other than the assessment of recruitment, treatment uptake and withdrawal from randomised treatment allocation after the 9-month internal pilot phase, and the assessments of clinical pregnancy and live birth rates in the control arm after 50% of randomised participants have been randomised and followed up for 15 months, respectively.

At the first interim assessment, the clinical pregnancy rate will be calculated in the control arm. If lower than the 10% estimate used for LBR in the control arm in the sample size estimation, sample size re-estimation will be considered, under the guidance of the DMEC. If greater than or equal to 10%, no adaptation will be made and the next interim assessment will take place when 50% of participants have completed the 15-month follow-up.

At the second interim assessment we shall calculate the LBR and its associated 95% CI for participants in the control arm. If the CI includes the 10% LBR (which we assumed for the control group in the sample size calculation) then we will continue to recruit to the original target sample size.

If the CI for the LBR in the control arm does not include 10% then we will re-estimate the sample size using the point estimate for the LBR we have observed thus far in the control arm and the same target difference of 10%. If this results in a reduction in the target sample size we will continue to recruit to the original target sample size (of N=560). If this results in an increase in the target sample size we will seek the opinion of the independent DMEC and TSC about increasing the sample size.

Baseline assessments

Baseline summary statistics will be reported by treatment arm and overall. Comparability between treatment arms (at randomisation or before interventions) will be descriptively reported without any statistical significance testing. Any observed differences in baseline characteristics and demographics believed to be important in confounding effectiveness evaluation of the intervention will be descriptively reported and adjusted for during sensitivity analyses described below.

Analysis of primary outcome

The primary outcome is the Live birth rate (LBR). This is defined by the number of live births after 24 weeks gestation within the 15-month post-randomisation follow-up period relative to the number of women randomised. Multiple live births (e.g. twins) will contribute one event to the numerator in the calculation of the live birth rate. The denominator for calculating the LBR will be the number of women randomised to each group. The primary binary outcome, the live-birth rate (LBR), will be compared between the two groups (hysteroscopic removal of submucous fibroids and endometrial polyps (Intervention) and no hysteroscopic removal (control)) using a Chi-squared test. A 95% confidence interval (CI) for the risk difference (RD) in LBR between the groups will also be calculated (37) using the recommended Wilson method. In consonance with the CONSORT guidance (38), the primary outcome will also be reported as maximum likelihood estimate (MLE) of the OR (Odds Ratio) with associated 95% CI based on a simple logistic regression model with the randomised group as the only predictor.

A complementary adjusted analysis will be undertaken using a multiple logistic regression model to account for stratification factors (centre and history of infertility/recurrent miscarriage) and potential confounding factors imbalanced at baseline. These variables will be treated as fixed

factors in the multiple logistic regression model. An adjusted MLE of the OR with associated 95% CI and p-value will be reported, to support the unadjusted results. Again, in consonance with the CONSORT guidance, the adjusted MLE of the RD will be estimated adjusted for randomisation stratification factors and covariates described above using one of the following approaches depending on convergence and model fitness;

- i. a Generalized Linear Model (GLM) (39) either with a Binomial or Poisson distribution and log link function through estimation of margins (40),
- ii. a GLM either with a Binomial or Poisson distribution and identity link function (41).

In either case, a GLM with a Binomial distribution will be the first choice. In the case of a GLM with a Poisson distribution, robust adjusted standard errors will be used (39–41).

Any noted differences between the unadjusted and adjusted primary analyses will be highlighted.

Missing primary outcome data

A default conservative ‘worst case’ scenario will be adopted as the primary approach for all the analyses, unless stated otherwise. Here, a woman whose live-birth outcome is unknown for some reason(s) contribute to a negative outcome, that is, they shall be assumed to have failed to produce a live birth. Due to multiple pregnancy, there is a possibility that some pregnant women may achieve multiple births resulting in potential multiple live births outcomes from a single mother. The default approach for dealing with multiple births for the primary analysis will be that a live birth is counted as a single event regardless of how many babies are born during that live birth.

A sensitivity analysis for the primary outcome, LBR, with missing birth outcome data, will be imputed through a “best” case (i.e. assume the woman had a successful live birth) and multiple imputation with chained equations and the results compared with the default analysis.

Non-compliance and contamination

Further sensitivity analysis for the primary outcome, LBR, will be undertaken to adjust for non-compliance and contamination (i.e. use of treatment by individuals in the control arm) using methods described in Cuzick et al (42) and the results compared with the default ITT analysis.

Analysis of secondary outcomes

Secondary binary outcomes such as the LBR at 24 months, multiple birth rate, implantation rate, clinical pregnancy rate, miscarriage rate, ectopic pregnancy rate, pre-term delivery rate and still

birth rate will be analysed in a similar way to the primary outcome. The denominator for the calculation of the rates will be number of participants randomised to the intervention and control arms respectively. We shall also repeat the above analyses on the per protocol population.

The ITT population (and safety) populations will consist of all women who consent and are randomised to receive or not receive hysteroscopic removal of submucous fibroids or endometrial polyps.

The per protocol population for those randomised to receive hysteroscopic removal of submucous fibroids or endometrial polyps is defined as a patient a) attending the clinic for the hysteroscopic excision of submucous fibroids and or endometrial polyps and b) receiving the procedure per protocol (following the sites usual procedures for hysteroscopic removal of submucous fibroids and / or endometrial polyps) within the first six-months post-randomisation. The PP population for those randomised to the control group and not to receive hysteroscopic removal of submucous fibroids or endometrial polyps is defined as a patient a) attending the clinic and b) not undergoing hysteroscopic removal of submucous fibroids or endometrial polyps procedure per protocol within the first six months post-randomisation.

Safety and adverse events

Adverse events including serious adverse events (death; hospitalization (initial or prolonged); disability or permanent damage; other important medical events), will be reported for each randomised group and compared between the two groups using a Fisher's Exact test or Chi-squared test (as appropriate). A 95% confidence interval (CI) for the difference in adverse event rate between the groups will also be calculated.

Sub-group analyses

An exploratory sub-group analysis using multiple logistic regression, with the primary outcome LBR, will look for an interaction between treatment group and the following sub-groups: a) infertility/recurrent miscarriage and b) type of fertility treatment received. A sub-group analysis looking at interaction between treatment group and type of submucous fibroid may be carried out if a sufficient number of control participants undergo diagnostic hysteroscopy, as part of site's usual diagnostic procedures, with fibroid type identified.

Analysis of time to event outcomes

Within the main trial period all women recruited to the trial will be followed up for a minimum of 2 years post-randomisation. Given the study recruitment will take 2.5 years then the first recruited women will have up to 4.5 years follow-up. Women will be censored at the last known date of follow-up if they have not had a live birth/clinical pregnancy.

Intervention waiting times and withdrawal from randomised treatment

The primary outcome analysis (the LBR at 15 months post-randomisation) may be affected by withdrawal or by women not receiving the randomised treatment allocation. That is if participants randomised to the intervention do not receive the resection by approximately 3-months post-randomisation we may not have a valid, reliable, and robust estimate of the effect of actually receiving the intervention. Rather we will just have an estimate of the policy of randomising participants to receive resection or not. Similarly, if participants randomised to the control treatment withdraw from the control treatment and receive a resection in the first 6-months post-randomisation then again we will not have a valid reliable and robust estimate of the effect of not receiving the intervention. If a substantial proportion of participants withdraw before 6 months post-randomisation or do not receive their treatment allocation by 3-post-randomisation then in these circumstances the comparison of the LBR outcome at 15 month post-randomisation outcome between the randomised groups may not produce a reliable and valid estimate of the effect of resection of fibroids / polyps or not.

The secondary outcome of time to live birth could also be affected by this. Statistical adjustment methods such as rank preserving structural failure time models and inverse probability weighting (IPCW) will be used to adjust for potentially informative withdrawal from randomised treatment (or withdrawal from the trial) in secondary analyses of the end of trial follow up data. These methods have been shown to perform well in a range of scenarios related to informative drop-out such as treatment crossover, though are associated with limiting assumptions (43–45). A subgroup analysis will include women with infertility/recurrent miscarriage. We also expect that IVF could be important and may differ between treatment arms. If this is the case we will undertake an analysis adjusting for IVF to estimate the relative effectiveness of surgery vs no surgery in the absence of IVF, using inverse probability of censoring weights.

Analysis of long term outcomes

We will also collect long term follow-up data from medical notes and / or NHS Digital for each participant after the trial has ended (minimum 5 years after each participant consented). The following data will be collected: number of live births; number of miscarriages; number of still births; number of terminations; whether or not the participant received hysteroscopy for endometrial polyps/submucous fibroids. The analysis of the count outcomes such as number of live births per single mother will be tabulated by treatment group to explore its distribution. The number of live births per single mother will be modelled as counts using either a Generalized Linear Model (GLM) with a log link function and: Poisson distribution or, Negative Binomial distribution in the presence of over dispersion; with the length of follow-up included in the model as an exposure variable. The mean incidence of live births per mother, Incidence Rate (IR), in

each treatment group over the study duration will be reported. The intervention effect will be reported as Incidence Rate Ratio (IRR) with associated 95% CI and P-value. An adjusted analysis will be undertaken to account for stratification factors (centre and history of infertility/recurrent miscarriage) and potential confounders, depending on the observed imbalance between treatment groups. The adjusted mean incidence of live births per mother, adjusted Incidence Rate (aIR), in each treatment group over the study duration will be reported. The intervention effect will be reported as adjusted Incidence Rate Ratio (aIRR) with associated 95% CI and P-value.

Health economic evaluation

The primary cost-effectiveness analysis will present costs per extra live birth, comparing the surgical interventions to control taking an NHS and personal social services perspective in accordance with NICE guidelines (46). Extra live birth will be used as the outcome instead of quality adjusted life years (QALYs) because QALYs are intended to capture improvements in health, not for placing a value on additional lives (47), as recognised in the NICE Clinical Guideline for Fertility (25). Resource use will include the intervention costs for hysteroscopy, expectant management costs, costs of IVF/IUI treatments and for those who conceive antenatal and post-natal visits, delivery costs and any hospital stays not related to birth for both mother and baby. Patient centered costs related to time taken to travel to appointments to receive the intervention (and the loss of productivity associated with attending such appointments), non-NHS funded fertility treatments, and for those who conceive antenatal and post-natal visits will also be collected for use in a secondary analysis that will take a societal perspective. Women will be asked to complete a resource use questionnaire at baseline, 6, 15 and 24 months post randomisation – each questionnaire will ask for data from the preceding 3 months. Women in the hysteroscopy arms will be asked to complete a patient cost questionnaire following their hysteroscopy for information only relating to their hysteroscopy. Unit costs will be derived from appropriate national sources and will include NHS reference costs and Personal Social Service Research Unit costs (48,49). The resource use questionnaire will be designed for this study and will draw on data collection tools developed in SchARR and those collated by the Database for Instruments for Resource Use Measurement (DIRUM). Two sets of economic analyses will be conducted – one based on an intention-to-treat analysis of the trial data, and another based on an analysis that adjusts for potentially informative withdrawal of randomised treatment or trial withdrawal. Results will allow for uncertainty using bootstrapping and probabilistic sensitivity analysis.

12. Trial supervision

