11.1 Sample size

The primary outcome for both trials will be live birth rate (LBR) defined by the number of live births after 24 weeks gestation within the 15-month post-randomisation follow-up period relative to the number of women randomised.

Our review of the research literature including a Cochrane review of hysteroscopic removal of submucous fibroids and endometrial polyps (6) has found no reported estimates of the LBR in our proposed target populations. Although, two previously conducted RCTs included in the Cochrane review roughly indicate a doubling of pregnancy rates. The first quoted a clinical pregnancy rate (at 6-7 weeks) of approximately 214/1000 (21%) over 12 months in a sample of 42 women with fibroids (submucosal and mixed submucosal intramural) without surgery and a miscarriage rate (between 7 and 12 weeks) in those without surgery of approximately 556/1000 (56%) (35). Applying the miscarriage rate to the pregnancy rate (i.e. $0.21 * 0.56$) would give a LBR of approximately 10% over 12 months in the control arm (no resection). The second, in women with endometrial polyps undergoing IVF, detected an increase of pregnancy rates from 28% to 63%, with no miscarriage rate reported (36). We therefore estimate a usual care LBR of 10% within 15 months in the populations of women proposed for inclusion in this study, both for the submucous fibroid and endometrial polyp RCTs.

Assuming a 10% LBR in the no hysteroscopic removal (control) group and that an absolute increase of 10%, to a 20% LBR (a relative risk of 2.00) in the hysteroscopic removal (intervention) group is of clinical and practical importance. Then to have a 90% power of detecting this difference or more, in LBR rates between the groups, as statistically significant at the 5% two-sided level, will require 266 women per group (532 in total). Adjusting for a predicted attrition rate of 5% (due to potential difficulties of follow-up for patients who have been referred from other NHS Trusts) we will require 560 participants to be randomised.

A similar sample size will be required for RCT2 (polyp population) i.e. 560 participants, so a total of 1120 participants are required for RCT1 and RCT2 combined.

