We will verify the 10% control group LBR used to inform the sample size calculation by conducting two interim assessments. The first interim analysis will be undertaken using the clinical pregnancy outcome once 50% of the target number of participants have been randomised. The clinical pregnancy outcome can be regarded as a proxy or surrogate outcome for the primary outcome the live birth rate, and allows for an earlier interim assessment to be made.. If the clinical

pregnancy rate outcome is greater than or equal to 10% we will continue to the 2nd interim assessment, using the primary outcome variable.. If the clinical pregnancy rate outcome is less than 10%, then the DMEC will then make a recommendation to the TSC regarding any need to alter the sample size of one or both of the trials.

Note: Clinical pregnancy rate is defined by an observation of viable intrauterine pregnancy with a positive heart pulsation seen on ultrasound at/after 8 weeks gestation

The 2nd interim assessment will be undertaken once 50% of randomised participants have been followed up for 15 months. With live birth data on approximately 50% (280/560 women per trial) we will be able to estimate the LBR within +/-5% (i.e. 95% CI: 5% to 15%). As we anticipate the endometrial polyp trial will recruit quicker than the submucous fibroid trial, and the control group LBR rate may differ between these two populations, this assessment will be undertaken in the two trials separately, at different time points. Both interim assessments will be undertaken by the DMEC, who will then make a recommendation to the TSC regarding any need to alter the sample size of one or both of the trials.

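### Under the absolute 10-point target difference, the first interim rule prompts sample-size review on the wrong side of 10%, and it sets a clinical pregnancy rate with no follow-up window against a live-birth threshold

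*Protocol*

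**What the plan says.** Protocol 11.1 plans each trial on "an absolute increase of 10%, to a 20% LBR (a relative risk of 2.00) in the hysteroscopic removal (intervention) group", with 90% power at the two-sided 5% level. This gives 266 women per group and 560 randomised after 5% attrition. The control figure comes from a small study reporting a "clinical pregnancy rate (at 6-7 weeks) of approximately 214/1000 (21%) over 12 months in a sample of 42 women" without surgery, combined with a miscarriage rate of about 56%. The protocol concludes: "We therefore estimate a usual care LBR of 10% within 15 months in the populations of women proposed for inclusion in this study".

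Two interim checks of the control rate follow.

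- **First interim.** Timing (11.1): "The first interim analysis will be undertaken using the clinical pregnancy outcome once 50% of the target number of participants have been randomised". Rule (11.2), applied to the control-arm clinical pregnancy rate: "If lower than the 10% estimate used for LBR in the control arm in the sample size estimation, sample size re-estimation will be considered", under DMEC guidance. Otherwise: "If greater than or equal to 10%, no adaptation will be made". No follow-up time is attached to the pregnancy rate. The 15-month follow-up belongs to the second interim only.
- **Second interim.** This takes place once half the participants have 15 months of follow-up and uses the control LBR with its 95% CI. If the CI excludes 10%, the size is recalculated with "the same target difference of 10" per cent. "If this results in a reduction in the target sample size we will continue to recruit to the original target sample size". If the recalculated size is larger, the DMEC and TSC are consulted.

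**The concern.** The first interim was added in version 5.0 so that sample size could be reconsidered earlier than live-birth data allow. Three features work against that purpose.

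- **Direction.** With a fixed absolute difference and rates below 50%, the variance grows with the control rate. A low control rate makes the trial over-powered, and a high one makes it under-powered. The rule reviews the first case and passes over the second.
- **Scale.** The quantity measured is clinical pregnancy, but the threshold is a live birth rate.
- **Maturity.** With no window, women randomised last week could count in the denominator with no chance of a recorded pregnancy, and the rate would then reflect how fast the trial recruited.

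At stake is the only check that comes early enough to change recruitment comfortably.

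**Working it through.** **1. The plan's own figure.** Inputs from 11.1: p1 = 0.10, p2 = 0.20, two-sided 5%, 90% power. Pooled two-proportion formula, with p̄ the mean of p1 and p2:

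n = [1.960·√(2p̄(1−p̄)) + 1.282·√(p1(1−p1) + p2(1−p2))]² / (p2−p1)²

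= [1.960·√0.255 + 1.282·√0.25]² / 0.01 = 265.9, so 266 per group. Then 532/0.95 = 560. Both match the protocol.

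**2. Direction.** The same formula with p2 = p1 + 0.10:

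| Control LBR | n per group | N with 5% attrition | Power at 266 per group | First interim, if the measured rate were the LBR |
|---|---|---|---|---|
| 5% | 188 | 396 | 97% | re-estimation considered |
| 10% | 266 | 560 | 90% | no adaptation |
| 15% | 335 | 706 | 82% | no adaptation |
| 20% | 392 | 826 | 76% | no adaptation |

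N must rise only where the rule does nothing. If a relative risk of 2.00 were held instead, the order reverses: 345 per group at 8% (power at 266: 81%) and 582 at 5% (59%).

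**3. Scale.** The planning study's 21.4% pregnancy and 55.6% loss give 0.214 × (1 − 0.556) = 0.095. The product printed in 11.1, 0.21 × 0.56 = 0.118, multiplies by the loss rate itself. Either way the protocol pairs about 21% clinical pregnancy with about 10% LBR. The pairing is approximate, because that study counted pregnancy at 6–7 weeks and this trial counts a heartbeat at or after 8 weeks.

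**4. Follow-up window.** Assumptions: 30 centres opening evenly over 7 months (8.1), Table 1 recruitment rates r, a constant conception rate giving 21.4% at 12 months (h = −ln(0.786)/12 = 0.0201 per month), and a 1.4-month lag to the 8-week scan. After month 7, cumulative recruitment is 30r(t − 3.5). At month 9 this gives 111 and 215, close to the protocol's 117 and 227. Half the target is reached at t = 3.5 + 280/(30r). The crude rate is the average of 1 − exp(−h(u − 1.4)) over follow-up times u, taken as zero for u below 1.4. The last column is the binomial chance of 13 or fewer pregnancies among 140 control women.

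| Scenario | 280 randomised at month | Mean follow-up (months) | Crude pregnancy rate | Chance below 10% |
|---|---|---|---|---|
| Fibroid, full target (0.67) | 17.4 | 7.1 | 10.6% | 36% |
| Polyp, full target (1.3) | 10.7 | 3.9 | 5.0% | 99% |
| Polyp, 40% of target (0.52) | 21.4 | 9.1 | 13.9% | 7% |

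The underlying conception rate is identical in all three rows. Only accrual speed differs.

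**5. Second interim as backstop.** Adding 15 months to the half-way point gives months 32.4, 25.7 and 36.4. Recruitment of 560 would end at 3.5 + 560/(30r), that is months 31.4, 17.9 and 39.4, against a planned 30 months. Under uniform accrual over 30 months, the second interim falls at month 15 + 15 = 30.

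**The case against.** The strongest reply is that the fixed 10-point difference and the commitment to keep 560 are written under the second interim. The first interim names no target difference, and 11.1 describes the effect both as an absolute increase and as a relative risk of 2.00. Held to the relative risk, a low-side trigger is sensible. This stands in part. A reader might infer that the first trigger can never lead to a needed increase, and the text does not go that far. But 11.1 bases N on the absolute difference and 11.2 holds it for re-estimation, so a relative-risk reading of the first interim contradicts the second.

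Three other inferences are also too strong:

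- *A 10% pregnancy rate means 4–5% LBR.* This applies the full 56% loss to pregnancies already past 8 weeks, and it comes from 42 women. On mature data, pregnancy is roughly an upper bound on LBR: a rate below 10% does contradict the planning value, while a rate above it settles nothing.
- *The polyp trial will raise a false alarm.* That depends on full-target accrual and on the fibroid study's 21.4% (11.1 quotes 28% for polyps). At 40% of target, already a green criterion, no trigger is expected. Nor does the model reproduce a 10% LBR at 15 months. Births by then need conception by about month 6, which gives 11% conceiving and, after 56% loss, about 5%. The protocol also fixes no interim denominator, so a crude rate over everyone randomised is one possible reading.
- *The plan ignores loss of power.* The second interim is two-sided and sends increases to the committees. It is late, not absent.

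Finally, a trigger only prompts DMEC advice, so a false alarm costs one review. That is fair and lowers the severity. It does not help above 10%, where 11.2 states that nothing will be adapted.

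**Conclusion.** The point holds in this form: under the absolute 10-point difference, the first interim considers re-estimation where none is needed and declines it where power falls, to 82% at a control LBR of 15% and 76% at 20%. The comparison also mixes two outcomes that the protocol itself places about twofold apart, and the missing window lets accrual speed move a crude rate between about 5% and 14% for one fixed conception rate. The sample-size figures rest only on the protocol's inputs. The accrual figures rest on even site opening, a constant conception rate and a crude denominator, and show sensitivity rather than a forecast. The second interim is a weak backstop because of its timing. This should be fixed, but it is not critical: the rule only prompts committee advice, and the primary analysis is unaffected.

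**What to change.** Reword 11.1 and 11.2 as follows:

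1. State that the absolute 10-point difference is held at both interims.
2. Estimate control-arm clinical pregnancy at a fixed time from randomisation, for example by Kaplan-Meier at 6 months, or only in women who have reached that visit.
3. Compare the estimate, with its 95% CI, with the clinical pregnancy rate at that same time that corresponds to a 10% LBR at 15 months. Use a pre-stated loss rate after 8 weeks and a sensitivity range.
4. Refer to the DMEC and TSC for a possible increase when the CI lies above that value. When it lies below, continue to 560, as the second interim already does. The CI matters: referral whenever the point estimate exceeded the value would fire about half the time when the assumption is true.

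Cost: protocol wording only, since pregnancy is already recorded at 6 months. The conversion rests on an assumed loss rate that the protocol does not supply, and the estimate is less mature than LBR. With fast accrual it will also be imprecise. At the full polyp target, women with 6 months of follow-up at the half-way point are those randomised by month 4.7, about (30 × 1.3/7) × 4.7²/2 ≈ 61, or roughly 30 controls. The timing of the first interim may therefore need to be set by follow-up reached rather than by numbers randomised alone.
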